Group 1: Investigators will attempt to identify potential subjects from those they have previously implanted at their individual practices. Investigators will review their records for consecutive subjects starting with those implanted closest to 8 years from the protocol approval date with the study components and moving forward in time. The Investigator should not skip any potential subject implanted with the appropriate combination of components. Potential subjects will be cross-sectioned using the methods described above. The Investigator should attempt to contact any previously implanted subject that satisfies the Inclusion/Exclusion Criteria until there is a total of 35 subjects enrolled collectively at all sites for each year window (+ 6 months).

Please note: previously implanted subjects with a pending revision of the WMT MoM components are eligible for enrollment and will need to be screened.

If a subject has appropriate WMT MoM components implanted in both hips, both can be enrolled in the study, as long as both hips satisfy the Inclusion/Exclusion Criteria. Subjects will be asked to sign two consent forms and complete two sets of questionnaires, one for each hip, but have only one blood draw and one MRI, if sufficient. Each THA will be assigned to the appropriate cross-sectioning interval (e.g. the two THAs may be in different intervals if bilateral THAs were not performed simultaneously).

Group 2 (Control Subjects): Investigators will attempt to identify potential control subjects from their individual practices as long as the subjects satisfy the Inclusion/Exclusion Criteria. Each subject can only be enrolled one time (see above for Group-2 enrollment guidelines).

Group 1 & 2: The Investigator will inform potential subjects of all aspects of the study, including all potential risks and benefits. Potential subjects will be allowed ample time to consider and ask questions about the information they have been provided. If after being informed the potential subject still wishes to participate, they will be asked to sign an Informed Consent document. Once the subject has signed the Informed Consent document and has met the Inclusion/Exclusion Criteria, they will be considered enrolled in the study. Any subject who signs the Informed Consent document and fails to satisfy the Inclusion/Exclusion Criteria will be considered a screen failure. Screen failures will be captured in the electronic data capture (EDC) system.

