I. Additional Follow-up Study Visit (Group 1 subjects diagnosed with ALTR only) An additional 1-year Follow-up Visit (Visit 2) will be required *only* for **Group 1** subjects who were diagnosed with ALTR at the first Study Visit (Visit 1). Subjects diagnosed with ALTR will remain enrolled in the study for up to one year following Visit 1 or until revised, whichever comes first. If a subject has not undergone a revision of the enrolled hip prior to the end of the one-year period, they will be re-evaluated with the HOOS, whole blood and serum metal ion levels, MARS MRI, and adverse event assessment during Visit 2. Subjects may have up to 4 weeks to complete the remaining activities due to scheduling logistics.

XIV. ADVERSE EVENTS AND ADVERSE DEVICE EFFECTS

A. Definitions

Adverse Event (AE) [1]

Any untoward medical occurrence, unintended disease or injury, or untoward clinical signs (including abnormal laboratory findings) in subjects, users, or other persons, whether or not related to the investigational medical device. This includes events related to the investigational device and procedures involved.

Adverse Device Effect (ADE) [1]

AE related to the use of a medical device. This includes events resulting from insufficient or inadequate instructions for use, deployment, implantation, installation, or operation, or any malfunction of the investigational medical device. This includes any event resulting from use error or from intentional misuse of the investigational medical device.

Serious Adverse Event (SAE) [1] AE that:

- 1) Led to death:
- 2) Led to serious deterioration in the health of the subject, that either resulted in
 - a. A life-threatening illness or injury, or
 - b. A permanent impairment of a body structure or a body function, or
 - c. In-patient or prolonged hospitalization, or
 - d. Medical or surgical intervention to prevent life-threatening illness or injury or permanent impairment to a body structure or a body function; or
- 3) Led to fetal distress, fetal death, or a congenital abnormality or birth defect

This includes device deficiencies that might led to a serious adverse event if (A) suitable action had not been taken or (B) intervention had not been made or (C) if circumstances had been less fortunate; and a planned hospitalization for pre-existing condition.

Serious Adverse Device Effect (SADE) [1]

Any ADE that has resulted in any of the consequences characteristic of a serious adverse event.

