- Mild: The AE is noticeable to the subject but does not interfere with routine activity and does not require medical treatment
- Moderate: The AE interferes with routine activity but responds to symptomatic therapy or rest. Usually requires medical treatment.
- **Severe:** The AE requires removal of the implant. The subject is at risk of death or loss of a limb.

E. Recording and Reporting Adverse Events

SAEs must be reported to MPO as soon as possible but no later than **10 calendar days** of the Investigator (or site personnel) becoming aware. This includes:

- All primary THA procedure related SAEs from time of THA implantation to the enrollment, and through subjects' study completion or withdrawal.
- If unable to provide as instructed, the Investigator (or site personnel) will notify Clinical Data Management at MPO (contact information listed in the Study Binder).

If a follow up report is required for a unresolved SAE it must be reported as soon as possible but no later than **10 calendar days** of the Investigator (or site personnel) becoming aware of additional information.

ADEs, UADEs , SADEs and USADEs must be reported to MPO as soon as possible but no later than **10 calendar days** of the Investigator (or site personnel) becoming aware. This includes:

- All UADEs, SADEs, and USADEs from the time of THA implantation through subjects' study completion or withdrawal.
- If unable to provide as instructed, the Investigator will notify Clinical Data Management at MPO (contact information listed in the Study Binder).

If a follow up report is required for unresolved UADEs, SADEs or USADEs it must be reported as soon as possible but no later than **10 calendar days** of the Investigator (or site personnel) becoming aware of additional information.

Upon MPO's request, the Investigator must supply any additional information related to the safety reporting of any event.

F. Adverse Event Status Update

The Investigator will follow subjects who experience an Adverse Event until it is resolved or the Investigator assesses them as chronic or stable or until the subject's participation in the study ends. Prior to completion of the study, the Investigator will document the resolution date. If surgical intervention is required to treat the AE, the Investigator will document the details of the intervention.

Any surgical interventions will be classified as follows:

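### The SAE definition lists planned admissions for pre-existing conditions as included, against its own requirement of an untoward event that led to serious deterioration

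*Protocol*

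**What the plan says.** Section XIV.A (Definitions) builds the SAE in layers. An AE is "Any untoward medical occurrence, unintended disease or injury, or untoward clinical signs". An SAE is an AE with one of three outcomes: death, serious deterioration, or fetal harm. The second outcome reads "Led to serious deterioration in the health of the subject, that either resulted in", and hospitalization is item c beneath it: "In-patient or prolonged hospitalization, or".

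A closing sentence extends the definition. It opens "This includes device deficiencies that might led to a serious adverse event if", gives three conditions (A) to (C), and ends after a semicolon with "and a planned hospitalization for pre-existing condition".

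Section XIV.E sets a limit of 10 calendar days for SAE reports to the sponsor and names as covered "All primary THA procedure related SAEs from time of THA implantation to the enrollment, and through subjects' study completion or withdrawal". Section XIII.A adds that "previously implanted subjects with a pending revision of the WMT MoM components are eligible for enrollment and will need to be screened". Section XI lists adverse events among the contents of the interim data looks, which go to FDA.

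**The concern.** A scheduled admission for a condition the subject already had is not in itself untoward or unintended, and it need not follow any worsening. The main part of the definition leaves it out and the closing sentence brings it in. Nothing elsewhere in the protocol settles which part governs.

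The definition is an operative rule. It decides what sites report within 10 calendar days, what must have a documented status at close-out (XIX.B), and what is counted as serious in the safety reporting of an FDA-ordered study. A target of 5 sites, up to 7, will apply it. If some follow the main part and others the added clause, part of any difference in SAE counts between sites would come from wording and not from patients.

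**Working it through.** The plan states no figure on this point and no arithmetic applies. The check sets the parts of the text side by side.

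1. **What the main part requires.** Two conditions must both hold: the event is an AE (untoward or unintended), and it led to death, serious deterioration or fetal harm. Hospitalization appears only as a result of serious deterioration.

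2. **What the closing sentence adds.** The semicolon followed by the conjunction makes planned hospitalization a second object of the opening verb, next to device deficiencies. It cannot be a further condition after (A) to (C), because it is a noun phrase and those are clauses. It carries neither a negation nor a limit to admissions with deterioration.

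3. **The two parts applied to typical records.**

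| Record | Main part | Closing sentence |
|---|---|---|
| Group 1 subject in ALTR follow-up, admitted for a long-scheduled operation on another joint, no worsening | Not an SAE | SAE |
| Group 1 subject enrolled with a pending revision, admitted as scheduled while on study | Depends on whether the underlying event meets a listed outcome | SAE, if the condition counts as pre-existing |
| Any subject admitted unplanned after a serious deterioration caused by an untoward event | SAE | Not needed |

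The first record is classified in opposite ways. The second shows a further gap: the protocol does not say whether a condition is pre-existing relative to implantation or to enrollment. A problem leading to revision usually lies between the two.

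4. **Who is exposed.** Sections X.E and X.G limit most subjects to one visit, with up to 4 weeks to finish activities. Only Group 1 subjects diagnosed with ALTR stay longer, for up to one year or until revision. A pending revision therefore falls on study only if it occurs within that short window or if the subject has ALTR. These two subgroups carry most of the effect. The protocol gives no expected number for either, so no count can be derived.

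5. **What depends on SAE status.** It governs the 10-day report, follow-up reports on unresolved SAEs, close-out, and the seriousness label in safety summaries. The primary endpoint (X.C) and the secondary endpoints (X.D) do not use it.

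**The case against.** The strongest reply is that the closing sentence is a deliberate extension. Its first item, a device deficiency that only might have led to an SAE, also fails the main part of the definition, so the sentence plainly adds categories. Since subjects with a pending revision are eligible, capturing planned admissions could be intended. This stands in part: the protocol alone does not show that a negation was lost. It does not remove the problem. On this reading too, elective admissions without deterioration are SAEs, reported and counted with true deteriorations.

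Second, the device signal has other protection. Each AE is rated separately for its relation to the device (XIV.B) and to the surgical procedure (XIV.C), and a SADE must first be an AE related to the device. Unrelated elective admissions can therefore be separated. This stands and limits the harm.

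Third, the only SAE scope that XIV.E spells out is procedure-related events, and an operation on another joint is not one. This stands in part, because the list is introduced as inclusive and may not be complete.

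Fourth, the case report forms are not shown, so divergence between sites is a risk and not a demonstrated fact. This stands.

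A reader might also infer that the index THA admission is itself an SAE for all 155 Group 1 hips, because the look-back starts at implantation. The documents do not support that. XIV.E covers events related to the primary procedure, not the procedure itself. Section XIII.C collects the index admission, operation and discharge dates separately as operative information. The protocol also does not say that every index admission was planned. Nor does the point carry much weight for controls: Group 2 subjects have no THA and leave the study after a single visit.

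**Conclusion.** Wrong as written, minor severity. The closing sentence of the SAE definition classifies as serious a kind of admission that the rest of the definition excludes, and no other section corrects it. The effect is confined to SAE counts and 10-day reporting, mainly for Group 1 subjects with ALTR and for those enrolled with a pending revision. The conclusion assumes that sites apply the text as printed and that no form guidance outside the pages at hand overrides it. The size cannot be stated as a number, because the protocol gives no rate of planned admissions and no expected number of subjects in these subgroups.

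**What to change.** In XIV.A, take planned hospitalization out of the inclusive sentence and state separately that a planned hospitalization for a pre-existing condition, without serious deterioration in health, is not an SAE. Say whether a condition is pre-existing relative to implantation or to enrollment. Add that any revision or removal of an enrolled hip is still recorded under XIV.F and judged against the SAE and SADE criteria on the event that led to it, so that the exclusion cannot drop device failures. Carry the same wording into the adverse event form guidance.

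The cost is a short protocol amendment, which under section XV needs FDA and IRB/EC approval. No new data are needed. Any SAE already entered only under the added clause would have to be re-coded.

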APPENDIX 3: Draft Case Report Forms (all Groups)

APPENDIX 4: Blood Draw and Metal Ion Analysis Protocol

APPENDIX 5: Imaging Protocol
